5.1.1.2 Per Protocol Population

The Per Protocol Population (PPP) is defined as all randomized subjects, who receive a complete treatment, and who complete the 5 month study without major protocol deviations. The PPP will be used for confirmatory analysis of the primary efficacy endpoint.

5.1.1.3 Safety Population

The Safety Population (SP) includes all randomized subjects in whom the treatment procedure is started, regardless of if the procedure is completed. The SP will be used for all of the safety summaries.

5.2. Statistical Analysis of Primary Measures

The primary efficacy endpoint for this study is CFB to 5 months post-treatment in 1-hour pad weight test. Analysis of covariance (ANCOVA) will be used, with treatment group and study site as independent variables and Baseline 1-hour pad weight as the covariate. Baseline 1-hour pad weight is defined as the 1-hour pad weight from the Baseline visit (Visit 2). The FAS will be used. Only observed case data will be used; that is, no imputation for missing data will be performed. The adjusted mean change (AMC) and standard error (SE) will be provided for each treatment group, along with the sham-AMC, 95% confidence interval (CI) and p-value for the Viveve Treatment group and for the cryogen alone treatment group. If the data is determined to be non-normally distributed, then a ranked ANCOVA will be used for the analysis.

A confirmatory analysis of the primary efficacy endpoint will be performed using the PPP.

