2. INTRODUCTION

Stress urinary incontinence (SUI) is a major challenge for many women particularly those who have experienced child birth or are menopausal. Upwards of 55% of women with a previous vaginal delivery may exhibit signs and symptoms of SUI (Tahtinen 2016). The overarching effects of SUI impact a women's health and quality of life and have been shown to result in depression, social stigma and lack of self-confidence. The need to use an external pad to absorb urine leakage from even normal daily activities such as laughing, or coughing is unsatisfactory and can be extremely inconvenient, and often embarrassing for women.

Currently available treatment options for women are limited. Pelvic floor exercises (such as Kegels) offer some benefit to a percentage of women but compliance and sustained benefit can be issues. More aggressive approaches to manage SUI include pelvic surgery, slings and mesh. These invasive options involve more risk and recovery time and are a last resort for many patients.

The gap between conservative and invasive treatment options for SUI represents an opportunity to address an enormous unmet healthcare need for women. Minimally invasive treatments for SUI would be a highly appealing solution provided they offered a safe, consistent improvement in symptoms without significant time commitment or recovery. Any effective treatment would represent a major advance in women's health.

The Viveve Procedure, SUI protocol, offers a non-surgical alternative to traditional surgery using non-ablative, monopolar radiofrequency (RF) energy to improve SUI. It induces a mild, controlled reaction in the submucosal tissues that stimulates the body to restore collagen, thereby remodeling the tissue without causing scarring.

This Statistical Analysis Plan describes the analyses planned for protocol VI-19-01 Amendment 2 version dated 15April2020, to demonstrate that the active treatment (i.e., Viveve Treatment, SUI protocol) is superior to the sham treatment.

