3. OBJECTIVES

3.1. Primary Objective

The primary objective of this single-blind study is to compare the effect of both the Viveve Treatment (RF plus cryogen) and cryogen alone treatment versus sham treatment, using the SUI treatment protocol (220 pulses), in improving mild to moderate SUI, assessed using the 1-hour pad weight test at 5 months post-treatment.

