5.3. Secondary Efficacy Analyses

The secondary efficacy endpoints include the CFB to 5 months post-treatment in total number of incontinence episodes as measured by the 3-day voiding diary, CFB to 5 months post-treatment in total number of pads utilized as measured with the 3-day

voiding diary, CFB to 5 months post-treatment in 24-hour pad weight, and CFB to 5 months post-treatment in I-QOL. The same ANCOVA that was used for the primary efficacy endpoint will be used for each of the secondary endpoints, with the relevant Baseline as the covariate. Baseline for each endpoint is the analogous measurement from the Baseline visit (Visit 2). The FAS will be used, with observed case data only. For each endpoint, the AMC and SE will be provided for all 3 treatment groups, along with the sham-adjusted mean change, 95% CI and p-value for the Viveve Treatment group and the cryogen alone treatment group. If, for any of the endpoints, the data is determined to be non-normally distributed, then a ranked ANCOVA will be used for the analysis.

For all of the secondary efficacy endpoints, a confirmatory analysis will be performed using the PPP.

The analyses described above for the primary and secondary efficacy endpoints will be carried out using SAS (Version 9.4 or above) Proc Mixed.

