5.5. Sample Size Justification

The primary efficacy endpoint for this study is the CFB to 5 months post-treatment in 1-hour pad weight. The study will compare both the Viveve Treatment (RF plus cryogen) and cryogen alone treatment versus sham treatment. The sample size for this study will be approximately 36 randomized subjects, in a 1:1:1 ratio. The sample size is expected to provide approximately 70% power to detect an effect size (difference in group means / standard deviation) of 1.06, and approximately 80% power to detect an effect size of 1.19, for the CFB to 5 months post-treatment in 1-hour pad weight between the Viveve Treatment and sham, and between the cryogen alone treatment versus sham.

Assuming a common standard deviation of 15, an effect size of 1.06 relates to a difference in means = 15.9, while an effect size of 1.19 relates to a difference in means = 17.9.

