5.6. Experiment Design and Randomization

5.6.1. Experimental Design

This is a randomized, single-blind, sham controlled multicenter clinical trial. This study is designed to evaluate the Viveve Treatment (RF plus cryogen, SUI protocol) and

Cryogen only treatment versus sham treatment for the primary efficacy endpoint, 1-hr pad weight test. Approximately 36 subjects (12 per treatment arm) who meet the entry criteria will be randomized on Day 1 in a 1:1:1 ratio to one of the treatment groups. The Viveve Treatment group will receive a therapeutic dose of 90 J/cm² of RF energy plus cryogen cooling, the Cryogen only treatment group will receive a sub-treatment dose of ≤ 1 J/cm² of RF energy plus cryogen cooling, and the sham group will be treated with an unpowered tip (i.e. treatment will be given without turning on the machine).

Subjects will be followed up with at 10 days and 5 months post-treatment. At the Baseline Visit and Month 5 Visit, subjects will be asked to provide a completed 3-Day Bladder Voiding Diary, complete a 24 hour pad-weight test, complete a 1-hour Pad Weight Test and I-QOL questionnaire. The subjects will be assessed for AEs at all study contacts and visits from the time the patient begins the treatment at the randomization visit.

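### Does the SAP need a planned Viveve versus cryogen-alone interval to do what it sets out to do?

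*SAP*

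**What the plan says.** The primary objective (SAP 3.1) is to "compare the effect of both the Viveve Treatment (RF plus cryogen) and cryogen alone treatment versus sham treatment". The Introduction states the aim as superiority of the active treatment over sham. SAP 5.5 gives power for two comparisons: "between the Viveve Treatment and sham, and between the cryogen alone treatment versus sham".

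SAP 5.2 fits an ANCOVA with treatment, site and baseline. It reports the adjusted mean change (AMC) and SE for every arm, and a sham-adjusted change with "95% confidence interval (CI) and p-value for the Viveve Treatment group and for the cryogen alone treatment group". SAP 5.3 repeats this for each secondary endpoint: "sham-adjusted mean change, 95% CI and p-value for the Viveve Treatment group and the cryogen alone treatment group". Both sections have a fallback, which 5.2 words as "If the data is determined to be non-normally distributed, then a ranked ANCOVA will be used for the analysis" and 5.3 as "If, for any of the endpoints, the data is determined to be non-normally distributed, then a ranked ANCOVA will be used for the analysis".

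The arms are described in SAP 5.6.1. Viveve receives 90 J/cm² of RF with cryogen cooling. For the second arm, "the Cryogen only treatment group will receive a sub-treatment dose" (at most 1 J/cm²), also with cooling. Sham is given with the machine off. The Introduction describes the procedure as "using non-ablative, monopolar radiofrequency (RF) energy to improve SUI".

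**The concern.** Viveve and sham differ in three things at once: RF, cooling and an active machine. Viveve and cryogen alone are both cooled, so theirs is the only pair that differs in RF dose with cooling held constant. A reader who sees the device described as working through RF would look for that difference, and neither 5.2 nor 5.3 lists it.

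The worry is that someone then compares the two sham p-values and reads a significant Viveve result beside a non-significant cryogen result as proof of an RF effect. That inference is invalid, because it does not estimate the difference between the two active arms. If the ranked ANCOVA were used, the model's outputs would be in ranks, and no difference in grams could be formed from them.

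**Working it through.** **1. The plan's own figures.** The inputs are 12 per arm (SAP 5.6.1), two-sided 0.05 (SAP 5.8), and effect sizes 1.06 and 1.19 with SD 15 (SAP 5.5). A two-sample t-test with 22 df has noncentrality d × √(12/2).
- Power at 1.06 is 69.9%, against about 70% stated.
- Power at 1.19 is 79.6%, against about 80% stated.
- 1.06 × 15 = 15.9 g and 1.19 × 15 = 17.85 g, which rounds to the stated 17.9 g.

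The sample size statement is therefore sound for the two sham comparisons that it names.

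**2. Which comparisons each section sets.**

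| SAP section | Comparison |
|---|---|
| 2 Introduction (aim) | active versus sham |
| 3.1 Primary objective | Viveve versus sham; cryogen alone versus sham |
| 5.2 and 5.3 Analyses | the same two |
| 5.5 Sample size | the same two |

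The sections agree. The sentence on RF in the Introduction describes the device and sets no hypothesis about RF apart from cooling.

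**3. How often the misleading pattern would arise.** Assume that both active arms have the same true effect, with 12 per arm and 31 residual df. In 1,000,000 simulated trials, Viveve is significant and cryogen alone is not in 13.6% of trials at 1.06 SD and 10.7% at 1.19 SD. These are frequencies of a pattern. They are not error rates of any planned test, because no section draws an RF conclusion from that pattern.

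**4. What the planned outputs already give under the plain ANCOVA.**
- Point estimate: AMC(Viveve) − AMC(cryogen). This is exact.
- Variance: SE(V)² + SE(C)² − 2 cov(V,C). The planned outputs give the first two terms but not the covariance, which is nonzero because site and baseline are in the model.
- Approximation: √(SE(V)² + SE(C)²).

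The approximation was checked on 20,000 simulated ANCOVA designs per setting. The assumptions were 2 or 3 equal sites, baseline uniform on 5 to 50 g, and either no loss or random loss to 30 evaluable. The ratio of approximate to direct SE was:

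| Evaluable | Central 95% of runs |
|---|---|
| 36 | 0.96 to 1.01 |
| 30 | 0.96 to 1.02 |

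Using the average of the two sham-contrast SEs as a stand-in is cruder. The ratio of the direct SE to that average runs from 0.95 to 1.05 with 36 subjects and from 0.90 to 1.10 with 30 (two sites). That wider range arises only if the planned per-arm SEs are ignored.

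**5. What this means in grams.** With 12 per arm and 31 df, the direct half-width is 2.0395 × 15 × √(2/12) = 12.49 g. With 30 evaluable, its median is 14.2 g. A 4% error in the SE is 0.04 × 12.49 = 0.50 g or 0.04 × 14.2 = 0.57 g.

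**6. The ranked fallback.** If ranks replace grams in the model, the Viveve-versus-sham and cryogen-versus-sham estimates move to ranks as well. The loss of scale is therefore not specific to Viveve minus cryogen alone. Adding a gram-scale interval for that one contrast would leave the two primary comparisons in ranks.

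**The case for a change.** The strongest case for acting is cost and timing. The direct contrast needs one more estimate from a model that is already fitted, with no extra subjects and no alpha. Fixing it now would prevent its inclusion and scale from being chosen after unblinding, and would discourage readers from comparing two p-values. Its exact SE is not among the planned outputs, and the SAP does not say whether estimates on the original scale are kept when ranks are used.

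Part of this stands. The contrast is absent from the SAP, it would be a reasonable descriptive addition, and anyone discussing RF should not rely on one significant and one non-significant sham comparison. None of this makes the plan wrong. The trial does not set the RF question, and the planned estimates and intervals already let a reader see how far apart the active arms are. At about ±12.5 g the direct interval might well be inconclusive. The silence on scale under the ranked ANCOVA is a question about the primary sham contrasts, and this contrast neither raises nor settles it.

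**Conclusion.** The concern does not hold. The aim, objective, analyses and sample size consistently specify comparison with sham, so leaving out a third contrast contradicts nothing and leaves no stated objective unanswered. A direct interval is a reviewer's preference, and adding it would change no planned result or conclusion.

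Under the plain ANCOVA the estimate is exact from the planned outputs. Its interval can be rebuilt to within about 0.6 g on a half-width of 12.5 to 14.2 g. That figure rests on SD 15 from SAP 5.5 and on the assumed number of sites, baseline distribution and random loss to 30 evaluable. The 13.6% and 10.7% figures describe a misreading that the SAP does not plan.

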5.3. Secondary Efficacy Analyses

The secondary efficacy endpoints include the CFB to 5 months post-treatment in total number of incontinence episodes as measured by the 3-day voiding diary, CFB to 5 months post-treatment in total number of pads utilized as measured with the 3-day

voiding diary, CFB to 5 months post-treatment in 24-hour pad weight, and CFB to 5 months post-treatment in I-QOL. The same ANCOVA that was used for the primary efficacy endpoint will be used for each of the secondary endpoints, with the relevant Baseline as the covariate. Baseline for each endpoint is the analogous measurement from the Baseline visit (Visit 2). The FAS will be used, with observed case data only. For each endpoint, the AMC and SE will be provided for all 3 treatment groups, along with the sham-adjusted mean change, 95% CI and p-value for the Viveve Treatment group and the cryogen alone treatment group. If, for any of the endpoints, the data is determined to be non-normally distributed, then a ranked ANCOVA will be used for the analysis.

For all of the secondary efficacy endpoints, a confirmatory analysis will be performed using the PPP.

The analyses described above for the primary and secondary efficacy endpoints will be carried out using SAS (Version 9.4 or above) Proc Mixed.

5.4. Statistical Analyses of Safety Measures

No statistical analyses will be performed on any of the safety data in this study. The SP will be used for all safety summarizations, with subjects included in the treatment group they actually received regardless of their randomized treatment group. AEs will be coded using definitions in the most recent version of Medical Dictionary for Regulatory Activities (MedDRA; Version 23.0). Each AE will be coded with its appropriate Preferred Term (PT), and linked with its associated System Organ Class (SOC). Based Section 3.3.2 of the Study Protocol (Section 4.1.3 of this document) all AEs are by definition treatment emergent (TEAE) so the term AE is equivalent TEAE. AEs will be summarized by SOC, severity, and relationship to study treatment for each treatment group.

No descriptive statistics are planned for vital signs or safety laboratory measurements, but data will be available in a listing. Screening data for the physical/pelvic/neurological examination will also not be summarized but will be provided in a listing.

5.5. Sample Size Justification

The primary efficacy endpoint for this study is the CFB to 5 months post-treatment in 1-hour pad weight. The study will compare both the Viveve Treatment (RF plus cryogen) and cryogen alone treatment versus sham treatment. The sample size for this study will be approximately 36 randomized subjects, in a 1:1:1 ratio. The sample size is expected to provide approximately 70% power to detect an effect size (difference in group means / standard deviation) of 1.06, and approximately 80% power to detect an effect size of 1.19, for the CFB to 5 months post-treatment in 1-hour pad weight between the Viveve Treatment and sham, and between the cryogen alone treatment versus sham.

Assuming a common standard deviation of 15, an effect size of 1.06 relates to a difference in means = 15.9, while an effect size of 1.19 relates to a difference in means = 17.9.

5.6. Experiment Design and Randomization

5.6.1. Experimental Design

This is a randomized, single-blind, sham controlled multicenter clinical trial. This study is designed to evaluate the Viveve Treatment (RF plus cryogen, SUI protocol) and

Cryogen only treatment versus sham treatment for the primary efficacy endpoint, 1-hr pad weight test. Approximately 36 subjects (12 per treatment arm) who meet the entry criteria will be randomized on Day 1 in a 1:1:1 ratio to one of the treatment groups. The Viveve Treatment group will receive a therapeutic dose of 90 J/cm² of RF energy plus cryogen cooling, the Cryogen only treatment group will receive a sub-treatment dose of ≤ 1 J/cm² of RF energy plus cryogen cooling, and the sham group will be treated with an unpowered tip (i.e. treatment will be given without turning on the machine).

Subjects will be followed up with at 10 days and 5 months post-treatment. At the Baseline Visit and Month 5 Visit, subjects will be asked to provide a completed 3-Day Bladder Voiding Diary, complete a 24 hour pad-weight test, complete a 1-hour Pad Weight Test and I-QOL questionnaire. The subjects will be assessed for AEs at all study contacts and visits from the time the patient begins the treatment at the randomization visit.

5.6.2. Randomization

Subjects will be randomized in a 1:1:1 ratio. Randomization will be stratified by study site, with a maximum of 20 subjects randomized at an individual site. Randomization codes will be generated over the entire study population. A randomization scheme will be employed with randomly permuted blocks. Randomization assignments will be generated by statistical software. The randomization number for each subject who is randomized will be assigned after confirmation of trial eligibility.

5.7. Handling of Dropouts and Missing Data

Subjects who discontinue the study prior to completion will not be replaced. Missing data will be considered left as missing.

5.8. Multiple Comparisons/Multiplicity

In this study, the Type 1 error is controlled at 0.05 two-sided for the primary efficacy endpoint.

The secondary efficacy endpoints will be compared to a significance level of 0.05 two-sided. No adjustment will be made for multiplicity for these endpoints. Given the number of comparisons, all p-values for secondary efficacy endpoints will be considered descriptive.

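### The SAP claims Type 1 error control at 0.05 for the primary endpoint, but its two unadjusted, unordered comparisons with sham give a family-wise error of about 9%

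*SAP*

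**What the plan says.** Section 5.8, the SAP's multiplicity section, makes an affirmative claim: "In this study, the Type 1 error is controlled at 0.05 two-sided for the primary efficacy endpoint". It names no procedure. For the secondary endpoints it says the opposite, "No adjustment will be made for multiplicity for these endpoints", and calls their p-values descriptive. The primary endpoint is thereby set apart as the controlled one.

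Three sections give that endpoint two comparisons:

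- Section 3.1 sets the primary objective: "compare the effect of both the Viveve Treatment (RF plus cryogen) and cryogen alone treatment versus sham treatment".
- Section 5.2 reports the sham-adjusted change with a "95% confidence interval (CI) and p-value for the Viveve Treatment group and for the cryogen alone treatment group".
- Section 5.5 gives its power for each active arm against sham.

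The Introduction (section 2) is narrower. It describes the purpose as "to demonstrate that the active treatment (i.e., Viveve Treatment, SUI protocol) is superior to the sham treatment" and does not mention cryogen alone.

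**The concern.** Section 5.8 claims control for the endpoint, not for each comparison. Two tests at 0.05 on the same endpoint do not control the endpoint at 0.05 if a win on either may be claimed, and the SAP has no success rule that prevents this. A significant result in either arm, including cryogen alone, could be reported as a controlled primary finding when the error rate behind it is almost twice the stated level.

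**Working it through.** **Inputs from the SAP**
- Allocation (5.6.1): "Approximately 36 subjects (12 per treatment arm) who meet the entry criteria will be randomized on Day 1 in a 1:1:1 ratio".
- Power (5.5), smaller effect: "approximately 70% power to detect an effect size (difference in group means / standard deviation) of 1.06".
- Power (5.5), larger effect: "approximately 80% power to detect an effect size of 1.19".
- Stated error level (5.8): 0.05 two-sided.

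**Step 1. Which alpha do the SAP's own figures assume?**
The SAP does not write that each primary comparison is tested at 0.05, so I checked this against the power statement. I used a two-sample t-test with n = 12 per arm, df = 2 × 12 − 2 = 22, and noncentrality δ = d × √(n/2) = d × √6.
- d = 1.06: δ = 1.06 × 2.449 = 2.60
- d = 1.19: δ = 1.19 × 2.449 = 2.91

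Power = P(|T| > t_crit), where T is noncentral t with 22 df:

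| Two-sided alpha per comparison | t_crit | Power at 1.06 | Power at 1.19 |
|---|---|---|---|
| 0.05 | 2.074 | 69.9% | 79.6% |
| 0.025 (Bonferroni) | 2.405 | 58.2% | 69.3% |
| SAP 5.5 | – | about 70% | about 80% |

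The SAP's figures match the unadjusted row and not the Bonferroni row. The 95% intervals in section 5.2 point the same way.

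**Step 2. Correlation between the two tests**
Each contrast of means has variance 2σ²/12. The two contrasts share the sham mean, so their covariance is σ²/12. The correlation is (σ²/12) / (2σ²/12) = 0.5.

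**Step 3. Family-wise error when both treatments equal sham**
FWER = P(|T₁| > t_crit or |T₂| > t_crit), each test at two-sided 0.05.
- If the tests were independent: 1 − 0.95² = 0.0975. This is an upper reference.
- Bivariate normal, correlation 0.5: 0.0907.
- Simulated with shared sham and pooled error variance: 0.090 at df 30 to 33, and 0.089 at df 22.

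Three arms of 12 leave 36 − 3 = 33 error df. The baseline covariate and the site terms lower this slightly. The SAP does not give the number of sites, so I used a range.

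Counting only false findings of benefit, the probability is 0.045, against 0.025 for a single two-sided 0.05 test.

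**Step 4. What each remedy does to power**
- Fixed sequence, Viveve first: the Viveve comparison keeps alpha 0.05 and its stated 70% and 80%. A formal cryogen-alone claim needs both tests to succeed. If both treatments have the planned effect, simulation gives about 57% at 1.06 and 70% at 1.19 (df 30 to 33), compared with 71% and 81% unadjusted on the same df.
- Dunnett: critical |t| is 2.31 to 2.32 at df 30 to 33, a per-comparison alpha of about 0.027. Power for each comparison is 61.5% and 72.5% at df 33 (59.7% and 70.8% at df 22).
- Bonferroni: 58.2% and 69.3% at df 22. About 15 per arm, 45 in total, would be needed to restore 70% and 80%.

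**The case against.** The best defence is that Viveve against sham is the only confirmatory test. The Introduction makes the SAP's one explicit superiority statement, and it names Viveve alone. Section 5.6.1 describes the cryogen arm as receiving a sub-treatment RF dose, which suits a component control. On that reading 0.05 is controlled. But no section labels cryogen alone as secondary or descriptive, and sections 3.1, 5.2 and 5.5 treat the two comparisons in parallel. If the single-test reading is intended, section 5.8 needs to say so.

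Three further points have some force:

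- The SAP gives no success rule at all, so a win on either arm is a possible reading and not a stated one. A rule that both must succeed would cause no inflation, but that is not written either.
- The 9% applies only when both treatments are null. If Viveve works, only the cryogen comparison can be a false positive, at 5%. The 9% also counts rejections in the direction of harm.
- Estimates and intervals are reported for both arms, so a reader could adjust the p-values afterwards. This limits the damage but does not make the claim in section 5.8 true.

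One point stands in full: a remedy confined to sections 5.8 and 5.2 would leave the power statement for cryogen alone in section 5.5 wrong.

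**Conclusion.** The concern holds. The SAP asserts control at 0.05 for the primary endpoint and contains nothing that provides it. Under the global null, with 12 per arm, a shared sham arm and each test at two-sided 0.05, the family-wise error is about 0.090, and the chance of a false finding of benefit is about 0.045 against 0.025. Testing each arm at 0.05 is an inference, but a well-supported one, from the 95% intervals and from power figures that reproduce only at that level. The result also rests on a claim being possible for either arm, which the SAP does not exclude. Because this concerns the error rate of the primary endpoint, it must be settled before unblinding.

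**What to change.** In section 5.8, with matching text in section 5.2, specify a fixed sequence. Test Viveve Treatment against sham first at two-sided 0.05. Test cryogen alone against sham at two-sided 0.05 only if the first test is significant; otherwise report its p-value and interval as descriptive. The order follows the purpose given in the Introduction.

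In section 5.5, state that the 70% and 80% power applies to the Viveve comparison, and that formal power for cryogen alone in the sequence is about 57% and 70% if both treatments have the planned effect.

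If both comparisons are to stand on equal terms, use Dunnett-adjusted p-values and confidence intervals for both instead, and restate the power in section 5.5 as about 61% and 72% per comparison.

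The cost is two sentences in sections 5.8 and 5.2 and one consequential edit in section 5.5. The fixed sequence needs no more subjects and leaves Viveve's power unchanged. Its price is that a formal claim for cryogen alone depends on Viveve succeeding first.
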